A Randomized, Double-blind, Placebo-controlled Study of the Use of Oral Cromolyn Sodium for the Treatment of Eosinophilic Esophagitis

Unique Protocol ID: 13-02521-FB

NCT02371941

Document Date: Created 3/21/2014

Document IRB approval 3/10/2015

Abstract

Eosinophilic esophagitis (EoE) is an increasingly prevalent disease that affects both children and adults. The disease is defined by both its clinical presentation and pathologic findings on biopsy. Pediatric patients typically present with abdominal pain, regurgitation, nausea, and trouble swallowing; with possible ultimate consequences of failure to thrive, food impaction, or esophageal wall rupture. The diagnosis must be confirmed with esophageal biopsy that shows eosinophilic infiltrates specific to the esophagus, after ruling out gastroesophageal reflux disease.

The goal of current therapies for EoE include resolving both tissue eosinophilia and symptoms and to prevent long-term consequences of the disease. The current therapies for EoE are limited to specialized diets and/or pharmacotherapy with swallowed, topical corticosteroids. Unfortunately, while both can be effective, each has its own limitations and risks. Specialized diets can be very difficult to adhere to, can potentially lead to malnutrition, and there is currently no perfect test to identify specific foods that should be removed from the diet. Topical corticosteroids, as an alternative to dietary therapy, can lead to systemic side effects, such as reduction in bone mineral density, poor growth, candidiasis, adrenal suppression, glaucoma, and cataracts. In addition, there is currently no data to suggest if, and when, patients can stop the specialized diets or the swallowed corticosteroids.

There is currently a great need for alternative therapies, especially for children with EoE. The ideal therapy would be effective, safe in children (preferably already studied in children for other conditions), cost-effective, and immune-modulatory. Cromolyn sodium, a medication approved for asthma and systemic mastocytosis, may be an ideal candidate therapy.

Hypothesis:

Oral cromolyn sodium, when made into a viscous preparation, will lead to a decrease in esophageal eosinophilia and in symptoms related to esophageal dysmotility in patients with eosinophilic esophagitis.

Specific Aims:

- 1. Specific Aim 1: To assess the efficacy of orally ingested viscous cromolyn sodium in reducing the esophageal eosinophilic infiltrate in children with eosinophilic esophagitis.
- 2. Specific Aim 2: To assess the efficacy of orally ingested viscous cromolyn sodium in reducing the symptoms associated with eosinophilic esophagitis in children.

Background and Significance:

Eosinophilic esophagitis (EoE) is a clinicopathologic disease that is increasing in prevalence in the United States.¹ The disease is defined by the presence of symptoms of esophageal dysmotility with concomitant findings of eosinophilic infiltrates (>15 eosinophils per high powered field on light microscopy) localized to the esophagus, in the absence of other

causes of esophageal eosinophilia (namely gastroesophageal reflux disease).² In the pediatric population, the disease typically manifests as abdominal pain, dysphagia, reflux, nausea, and vomiting; a symptom pattern that can lead to failure to thrive.³ While few natural history studies exist, available data suggest that if left untreated, EoE may lead to food impactions requiring emergent removal food boluses and possible esophageal wall rupture.⁴⁻⁵

The exact etiology of EoE has not yet been elucidated, however most data suggest that the disease is immune-mediated and antigen-driven. This has been proven clinically by demonstrating that the majority of patients will have resolution of both symptoms and histologic findings after treatment with an amino-acid based formula that is devoid of protein antigens.⁶⁻⁷ In addition, most patients with EoE show an immune deviation that differs from healthy controls.⁸ A genome wide association study has shown common variants at chromosome 5q22, the location of the thymic stromal lymphopoeitin gene, a gene associated with immune skewing toward a T-helper (Th) type 2 response.⁹ In addition, expression of eotaxin-3, interleukin(IL)-4, and IL-5 (Th2 cytokines) have all been shown to be increased in patients with active EoE.¹⁰ These findings suggest that patients with EoE have a genetic predisposition that leads them to an aberrant Th2 type response to non-pathogenic antigens. As would be expected from this hypothesis, the majority of patients with EoE, have some form of atopic/allergic disease.¹¹

Currently, Treatment options for patients with EoE include dietary therapy and/or pharmacotherapy.² Dietary therapy consists of avoiding antigenic triggers of the disease, and can be in the form of an elemental diet or an elimination diet. An elemental diet can be very difficult to adhere to, even for infants and toddlers, as it allows the patient to only ingest an amino acid-based formula and one other food as their source of nutrition. The elimination diet is more flexible, and can be based on testing or can be done empirically by removing common food triggers (namely milk, egg, soy, wheat, nuts, fish, and shellfish). Unfortunately, there are currently no reliable tests to predict which foods will be the trigger in any given patient, and therefore trial and error of food elimination and re-introduction must constantly be undertaken.

Pharmacotherapy for EoE entails swallowing topical corticosteroids, with the goal of prolonged exposure of the corticosteroid to the esophagus, thus limiting systemic absorption. In fact, double-blind, randomized, placebo-controlled trials have shown efficacy of both swallowed fluticasone and swallowed budesonide.¹²⁻¹³ Unfortunately, there is no consensus on the duration of therapy, and studies to date have shown recurrence of eosinophilia and symptoms within months of stopping therapy, even with addition of steroid-sparing agents, such as montelukast.¹⁴⁻¹⁵

Given that none of the current treatment options are ideal, there is clearly a need for novel and effective therapies for EoE. One candidate therapy that is yet to be studied is oral cromolyn sodium. Oral cromolyn is an attractive alternative to swallowed steroids for EoE for a number of reasons.

First, oral cromolyn has minimal to any systemic absorption. In fact, in studies of adults and children, less than 1% of orally administered cromolyn gets absorbed.¹⁶ Due to this, cromolyn is a first line agent in the treatment of the gastrointestinal manifestation of systemic mastocytosis, but not for the systemic manifestations of the disease. Second, due to its poor absorption, the side effect profile of cromolyn sodium is almost non-existent, and it is FDA-approved for use down 2 years of age.¹⁷ Third, data exist to show increased numbers of mast cells in the esophageal tissue of patients with EoE, and that these mast cells are associated with smooth muscle contraction, and thus are perhaps the cause of the symptomatology of EoE.¹⁸ Therefore, by targeting and stabilizing mast cells (the major action of cromolyn), in addition to

eosinophils, one may be able to effectively treat EoE with non-steroid medications. Finally, cromolyn, when inhaled and used in asthmatics, causes a reduction in sputum eosinophils; and the clinical benefit in asthma has been directly linked to a reduction in eosinophils in bronchial alveolar lavage specimens.¹⁹ This suggests that in addition to its known mast cell stabilizing properties, cromolyn exerts some effect on eosinophils as well. In fact, after 16 weeks of treatment with inhaled cromolyn, researchers have shown a significant decrease in activated eosniophils in bronchial submucosa; an effect that was similar to treatment with fluticasone propionate, but not seen with placebo or salmeterol (a long acting β 2-agonist).²⁰

Given these properties of cromolyn sodium, we propose that it would be an ideal candidate to investigate as a treatment option for patients with EoE.

Protocol Design and Experimental Methods:

The proposed research protocol design is a randomized, double blind, placebo-controlled trial to determine if oral administration of viscous cromolyn sodium will be effective in the treatment of eosinophilic esophagitis.

Primary Outcome Measure:

The primary outcome measure will be the change in esophageal eosinophilia after 8 weeks of treatment with cromolyn as compared to placebo.

Secondary Outcome Measures:

- 1. The change in symptoms scores from baseline and at weeks 0, 4, and 8.
- 2. The incidence of adverse events throughout the study

Inclusion Criteria:

- Established diagnosis eosinophilic esophagitis.
- >2 years of age, < 18 years of age

Exclusion Criteria:

- Concomitant treatment with swallowed corticosteroids. Any prior use of swallowed corticosteroids will require a 4 week washout period.
- Pregnancy
- Evidence of pathologic eosinophilia in other locations in the GI tract.
- Participation in another research protocol
- Renal or Hepatic Insufficiency

Study Medication

The study medication is oral cromolyn sodium, made into a viscous preparation by the addition of powdered sugar.

The medication is supplied as a 100 mg/5 mL suspension and should be made into a thickened slurry prior to ingestion with 1 tablespoon of powdered sugar. This should also make the medication more palatable for children.

Dosing will be 100 mg 4 times daily for children ages 2 - 12 years of age and 200 mg 4 times daily for children ages 12 - 18 years of age. The medication should be taken 30 minutes before meals and before bedtime.

This dosing regimen is based on current dosing strategies for systemic mastocytosis.

Randomization /Placebo Administration

Cromolyn/Placebo will be administered in a blinded fashion. The pharmacist will perform the randomization and will allocate 8 weeks of cromolyn/placebo to the patient. The patient and physicians caring for the patient will be blinded as to which medication the patient is receiving.

Symptom Scores

Symptoms will be assessed at baseline, week 4, and week 8 by the patients and caregiver. This will done using an established symptom scoring diary known as the Pediatric Eosinophilic Esophagitis Symptom Score (PEESS).²¹ Figure 2.

FIGURE 2. The Pediatric Eosinophilic Esophagitis Symptom Score

FREQUENCY	Never	1-3/month	Once/week	2-6/week	Daily	>1/Day
Nausea	0	1	2	3	4	5
Vomiting	0	1	2	3	4	5
Abdominal Pain	0	1	2	3	4	5
Chest Pain	0	1	2	3	4	5
Heartburn	0	1	2	3	4	5
Regurgitation	0	1	2	3	4	5
Dysphagia	0	1	2	3	4	5
Food impaction	0	1	2	3	4	5
Poor appetite	0	1	2	3	4	5
Early Satiety	0	1	2	3	4	5

Symptom Score

Frequency Score (add all circled entries):

SEVERITY	None	Mild	Moderate	Severe
Nausea	0	1	2	3
Abdominal Pain	0	1	2	3
Chest Pain	0	1	2	3
Heartburn	0	1	2	3
Dysphagia	0	1	2	3
Poor appetite	0	1	2	3
Early Satiety	0	1	2	3
Inadequate	0	1	2	3
weight gain				

Severity Score (add all circled entries and multiply x2):

Total score:

In past studies using this diary, parents/caregivers helped with the survey for younger children <10 years of age, and children older than 10 years of age were typically able to complete it on their own.

Monitoring During Study

Patients will have a baseline physical exam performed at the initial study visit by the principal investigator. They will be supplied with 8 weeks of study medication to be administered at home. They will have a study visit (Visit 2) done at week 4 for recording of vital signs, review of adverse events, and symptom assessment. Finally they will have a physician visit at the 8 weeks for physical exam and endoscopy with biopsies.

Adverse events will be recorded on a blank calendar for each month that the patient is enrolled in the study.

Endoscopy with biopsy:

All qualifying subjects will have had an upper gastrointestinal endoscopy with biopsies performed prior to the baseline visit to establish a diagnosis of EoE. As part of routine clinical care, all subjects will again have post-therapy endoscopy with biopsies performed at week 8.

[figure not shown]
Allergy Skin Prick Testing:

As part of routing clinical care, all patients will have allergy skin prick testing performed to evaluate for environmental and food allergies. The allergens tested will be tree pollens, grass pollens, weed pollens, molds, dust mite, cockroach, cat, dog, milk, egg white, soy, wheat, peanut, walnut, shrimp, and catfish.

Study Protocol and Timeline:

The proposed study timeline is shown in Figure 3.

Figure 3. Study Timeline

The a priori power of the primary end-point analysis was estimated using Fisher's exact test with .05, two-tailed significance level. Assuming a histologic response rate of 80% in the oral viscous cromolyn group and 10% in the placebo group, there was 85% power to detect a significant between-group difference with sample sizes of 10 subjects in each group.

REFERENCES:

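### Swallowed steroids are excluded and washed out, but the readable protocol neither requires a stable diet nor records diet between the two biopsies; diet changes could dilute the treatment difference by an amount that cannot be estimated

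*Combined protocol and SAP*

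**What the plan says.** The Abstract describes the treatment landscape: "The current therapies for EoE are limited to specialized diets and/or pharmacotherapy with swallowed, topical corticosteroids". Of these two, the Exclusion Criteria restrict only the steroids: "Concomitant treatment with swallowed corticosteroids. Any prior use of swallowed corticosteroids will require a 4 week washout period". No readable inclusion criterion, exclusion criterion or conduct section mentions diet.

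Background and Significance gives the reasons why diet could matter, and some reasons for caution:

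- On elemental diet it says that "the majority of patients will have resolution of both symptoms and histologic findings after treatment with an amino-acid based formula", but also that "An elemental diet can be very difficult to adhere to, even for infants and toddlers".
- On elimination diet it says: "The elimination diet is more flexible, and can be based on testing or can be done empirically by removing common food triggers". It gives no response rate for this diet and says that no test reliably identifies a child's trigger foods.
- Managing by diet means that "trial and error of food elimination and re-introduction must constantly be undertaken".

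Monitoring During Study has a physical exam at the first visit, and a physical exam and endoscopy at week 8. For the visit between them it says: "They will have a study visit (Visit 2) done at week 4 for recording of vital signs, review of adverse events, and symptom assessment". Diet is not listed at any visit. Allergy Skin Prick Testing has every child tested in routine care, including for eight foods, and gives no rule on acting on the results. Endoscopy with biopsy dates the first biopsy only loosely: "All qualifying subjects will have had an upper gastrointestinal endoscopy with biopsies performed prior to the baseline visit to establish a diagnosis of EoE". No maximum interval before baseline is stated.

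The timeline (Figure 3) is not shown in the text available, so a diet item there cannot be ruled out.

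**The concern.** The primary outcome is the change in esophageal eosinophilia after 8 weeks, and the power statement is written in terms of histologic response. By the protocol's own account, a treatment that can alter histology is left free to vary between the two biopsies. Because the first biopsy has no dated window, that period is longer than 8 weeks.

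Two kinds of change matter. If children in both arms start a diet, extra responders appear mainly on placebo, where more children can still respond. If children re-introduce foods, responders are lost mainly on cromolyn, where there are more to lose. Either way the difference between arms shrinks. The trial has 10 children per arm and little power to spare. A diet change that nobody wrote down cannot be recovered at analysis, so its part in the result could not be judged.

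**Working it through.** **Inputs from the protocol** (paragraph on power, under Study Protocol and Timeline): two-sided Fisher's exact test, alpha 0.05, response 80% on cromolyn and 10% on placebo, 10 per arm, stated power 85%.

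**Inputs assumed**, because the documents give none: a share d of children starts a diet and a fraction r of those who would not otherwise respond then do so. For re-introduction, the same values are used for the share who re-introduce foods and the fraction of responders among them who lose response. The illustration takes d = 5% and 10%, r = 20% and 30%, the same in both arms. Write k = d × r.

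**Step 1. The plan's own figure.** Sum the probabilities of all pairs of Binomial(10, 0.8) and Binomial(10, 0.1) counts with Fisher p ≤ 0.05. Power is 84.1%, which agrees with the stated 85% to within rounding.

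**Step 2. Formulas.**

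- Diet started, planned rates containing no diet response: p′ = p + (1 − p)k. This gives 0.8 + 0.2k against 0.1 + 0.9k.
- Foods re-introduced: p′ = p(1 − k).
- Both, in different children, k each way: p′ = p(1 − k) + (1 − p)k.

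For example, d = 10% and r = 30% give k = 0.03. Diet starts then give 0.806 against 0.127, a difference of 67.9 points instead of 70.

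**Step 3. Exact power at 10 per arm.**

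| d | r | k | Diet starts | Re-introduction | Both |
|---|---|---|---|---|---|
| 5% | 20% | 0.010 | 82.8% | 83.1% | 81.7% |
| 5% | 30% | 0.015 | 82.1% | 82.6% | 80.4% |
| 10% | 20% | 0.020 | 81.4% | 82.0% | 79.0% |
| 10% | 30% | 0.030 | 80.0% | 81.0% | 76.3% |

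Diet starts cost 1.4 to 4.2 points. They correspond to 1 to 2 changers in 20 children (20d) and 0.2 to 0.6 expected diet responses (20k, an upper figure because some of those children would respond anyway). At 11 per arm, power with diet starts is 87.4% to 89.5%, above the planned value in all four cases.

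**Step 4. Break-even for diet starts.** Only k matters. Power falls below 80% at k of about 3%, below 75% at 6.5% and below 70% at 10%.

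**Step 5. A case with no loss.** If the planned 10% placebo rate, and likewise the 80%, already include responses due to diet, starting diets leaves power at 84.1%.

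**Step 6. Type I error.** With a common response rate in both arms, the largest rejection probability of this test at 10 per arm is 1.28% (at a rate of 50%). Diet changes that do not depend on allocation move both arms to some common rate under the null, so they cannot push the error above this.

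**The case against.** Nothing in the documents shows that diets will change. The remark about trial and error describes the burden of managing by diet, not conduct in this trial. The only histologic evidence quoted is for elemental formula, which the protocol calls hard to adhere to. Skin-test results trigger no stated action, and the protocol itself says no test reliably identifies the triggers. All of this stands: diet change is possible, not shown to be likely.

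The illustrated loss is also modest. A true cromolyn rate of 75% instead of 80% would give 75.9% power, slightly worse than the worst combined diet case (76.3%). That stands too, and it limits how much weight the point can carry.

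A reader might infer that diet changes will certainly lower power. The documents do not support that. The 10% placebo rate may already allow for diet response. Blinding makes similar changes in the two arms the natural expectation, but chance imbalance is possible with 10 per arm, and diet responses falling only in the cromolyn arm would raise power.

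A reader might also infer a large loss. If k were 5% to 30%, diet starts would give 77.1% down to 42.7%. With r of 20-30%, however, k = 5% already needs 17-25% of children to start a diet (0.05/0.30 to 0.05/0.20), and k = 30% needs all of them at r = 30%.

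Finally, 8/10 against 1/10 gives p = 0.0055 and 8/10 against 3/10 gives p = 0.070, so it is tempting to say that two extra placebo responders would remove significance. Under the illustrated inputs each placebo child is converted with probability 0.9k, and the chance of two or more conversions among 10 is only 0.3% to 2.8%. The statement also holds cromolyn at 8/10; at 9/10 against 3/10, p = 0.020.

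The objection does not answer the missing record. Whatever the true rate, an unrecorded change cannot be taken into account later.

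**Conclusion.** The gap is real in the readable text: one of the two therapies the protocol names is controlled, and the other is neither controlled nor recorded. Diet changes similar in both arms could dilute the between-arm difference and lower power by an amount the documents do not allow one to estimate. The illustration runs from 84.1% to about 83-76%. It rests on assumed values of d and r, on equal effects in both arms, and on planned rates that contain no diet response; if they do contain it, diet starts cost nothing.

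A reader might infer that the comparison is biased or its false-positive rate inflated. Randomisation and the blinding of patients and treating physicians argue against that, and the exact test stays at or below 1.28%. What is at stake is some power and the ability to interpret a 20-child result. This is worth fixing because it is cheap, not because the trial is invalid without it. Confidence is medium, given the undisclosed rates and the timeline that is not shown.

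**What to change.** By one protocol amendment:

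- Record current diet and any change, with date and reason, at baseline, week 4 and week 8. This alone resolves the interpretation problem.
- Add a criterion that diet, including any existing elimination diet, is kept stable from the qualifying biopsy to the week-8 biopsy, unless a change is clinically necessary (for example, after an immediate food reaction).
- State that non-urgent action on food skin-test results waits until after the week-8 biopsy.
- Keep children who change diet in their randomised arm with their observed biopsy result, and report changes by arm descriptively. Do not add an analysis that counts them as non-responders.

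The primary test and the 4-week steroid washout stay as they are.

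The cost is one criterion, one sentence on skin tests and one data item at three existing visits, with no added procedures. There are two downsides. Eligibility becomes slightly narrower, because children whose diet changed after the qualifying biopsy are left out, and the documents do not let one estimate how many. For some children, a diet change is deferred by up to 8 weeks after baseline.

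### Age 12 ends one dosing band and starts the next: does the plan need to change?

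*Combined protocol and SAP*

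**What the plan says.** The Study Medication section sets the dose by age in one sentence. Its lower band is "100 mg 4 times daily for children ages 2 - 12 years of age"; its upper band, in the same sentence, is "200 mg 4 times daily for children ages 12 - 18 years of age". It adds that the regimen follows dosing practice in systemic mastocytosis, and gives the strength: "The medication is supplied as a 100 mg/5 mL suspension".

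The Inclusion Criteria admit children ">2 years of age, < 18 years of age", so a 12-year-old can enrol. Under Randomization /Placebo Administration, "The pharmacist will perform the randomization and will allocate 8 weeks of cromolyn/placebo to the patient". No section puts an inequality at 12, says whether age means completed years or exact age, or fixes the date on which age is taken.

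Background and Significance says that "less than 1% of orally administered cromolyn gets absorbed" and that "the side effect profile of cromolyn sodium is almost non-existent". The power statement, after the study timeline, rests on "sample sizes of 10 subjects in each group".

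**The concern.** A dosing rule should send each eligible child to exactly one dose. Here 12 closes the lower band and opens the upper one, and the doses differ by a factor of two. If age means completed years, the rule gives two answers for every child between the 12th and 13th birthdays. Eight weeks of supply are allocated to each patient, so whichever answer is taken would hold for the whole treatment period.

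Two careful people could therefore dose the same child differently. If that happened often, or differently by arm, the active arm would carry an unplanned mix of doses, and one might worry about the comparison or the blind.

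**Working it through.** **1. The plan's own figure.** Inputs from the power statement: response 80% against 10%, 10 per group, Fisher's exact test, two-sided 0.05. Take all 11 × 11 = 121 possible pairs of responder counts and add up the binomial probabilities of those with p ≤ 0.05. The power is 0.841, about one point below the stated 85%, so the figure is reproduced. No input is an age or a dose; the 80% is assumed for the cromolyn arm as a whole, across both bands.

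**2. Size of the difference at age 12.** The strength is 100 mg / 5 mL = 20 mg/mL, and 8 weeks is 56 days.

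| | Lower band | Upper band |
|---|---|---|
| Daily dose | 100 × 4 = 400 mg | 200 × 4 = 800 mg |
| Volume per dose | 100 / 20 = 5 mL | 200 / 20 = 10 mL |
| Volume over 8 weeks | 5 × 4 × 56 = 1,120 mL | 10 × 4 × 56 = 2,240 mL |

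**3. Which reading of age fits the text.** Set the eligibility limits (above 2, below 18) beside the bands (2 to 12, 12 to 18).

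- *Exact age.* The bands cover the eligible range without a gap. The figures 2 and 18 are its outer limits, and 12 is the cut between the bands. The only overlap is the 12th birthday.
- *Completed years.* An age above 2 would mean 3 or more, so the lower band would start at a class that cannot enrol, although the Background cites approval from age 2. The upper band would end at 18, which cannot enrol either. The text would then disagree with itself at 2 and 18 as well as at 12.

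Exact age is the better fit. This is an inference; the documents do not say so.

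**4. How often it could arise.** The documents give no age distribution, so the shares below are assumptions. The chance of at least one such child is 1 − (1 − p)^n.

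- *Exact age*, uniform over 18 − 2 = 16 years: p = 1 / (16 × 365) = 0.00017. The expected number among 20 is 20 × 0.00017 = 0.0034.
- *Completed years*:

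| Assumed share aged 12 | Expected of 10 (active arm) | At least one of 10 | Expected of 20 | At least one of 20 |
|---|---|---|---|---|
| 3% | 0.3 | 26.3% | 0.6 | 45.6% |
| 6.25% (1 of 16 years) | 0.63 | 47.6% | 1.25 | 72.5% |
| 10% | 1.0 | 65.1% | 2.0 | 87.8% |

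These are chances that a 12-year-old enrols. They are not chances of a dosing error or of a changed result.

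**5. Effect on the comparison.** Age is fixed before randomization and does not depend on arm. A 12-year-old on either dose stays in the arm drawn and contributes one response to the 2 × 2 table. Nothing in the validity of Fisher's test depends on which band was used.

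**The case for a change.** The best case for acting is that the rule is open on its face and cheap to close. The protocol writes strict inequalities for eligibility but none at the dose cut. People often give age in whole years, and on that reading the trial would more likely than not meet a 12-year-old at a share of 6.25% or more.

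Exact age also leaves a question: is the band fixed at the start, or does it move for a child who turns 12 on study? With uniform ages the share is 0.0625 × 56 / 365 = 0.0096, and the chance of at least one among 20 is 1 − (1 − 0.0096)^20, about 17.5%.

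Finally, only the patient and treating physicians are named as blinded, and the pharmacist who randomizes might also be the one to settle the dose.

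What stands: the wording is imprecise at 12, the date at which age is taken is unstated, and a line of text would cure both. What does not stand is the step from there to the trial's results. The section does not say who assigns the band, and nothing suggests the overlap would be settled differently by arm. Placebo volume is not described at any age, so the overlap did not create that question. The documents show no specific harm from either planned dose.

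**Conclusion.** The overlap is real but clerical, and the plan's design and analysis stand as they are. At most it concerns children aged 12, who would receive 400 or 800 mg/day, both planned doses. On the reading that best fits the eligibility limits, it concerns a single birthday. Writing down a boundary would change no estimate, test, sample size or power, and staff can settle the point from the mastocytosis practice that the protocol names as its basis.

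The conclusion rests on three things: exact age as the better-supported reading, an assumed age distribution for the frequencies, and the protocol's own account of absorption and side effects. If completed years were intended, the overlap would arise more often, but its effect on the comparison would be no different. The two bands still have to be reconciled, with the age convention and reference date, when dispensing is set up. Which band takes age 12 is for the sponsor and investigator, and no view is offered here.

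### The 85% power belongs to a histologic responder rate that the plan does not define and does not link to its stated primary outcome, the change in eosinophilia

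*Combined protocol and SAP*

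**What the plan says.** The Primary Outcome Measure section reads: "The primary outcome measure will be the change in esophageal eosinophilia after 8 weeks of treatment with cromolyn as compared to placebo". The Hypothesis (treatment "will lead to a decrease in esophageal eosinophilia") and Specific Aim 1 (efficacy "in reducing the esophageal eosinophilic infiltrate in children with eosinophilic esophagitis") use the same language of reduction.

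The power statement, which follows the Figure 3 caption under Study Protocol and Timeline, describes a different kind of variable. It says "The a priori power of the primary end-point analysis was estimated using Fisher's exact test with .05, two-tailed significance level", then "Assuming a histologic response rate of 80% in the oral viscous cromolyn group and 10% in the placebo group", and concludes that "there was 85% power to detect a significant between-group difference with sample sizes of 10 subjects in each group".

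Histologic response appears only in that statement. The one eosinophil threshold in the readable text, ">15 eosinophils per high powered field on light microscopy", is in Background and Significance, where it is part of the definition of the disease. No other readable section names a test for the primary outcome.

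**The concern.** Fisher's exact test compares proportions, so it needs each patient classed as responder or non-responder. The plan gives no count at or below which a patient has responded. It also gives no count basis (peak or mean, and over which biopsies). Until these are set, the test named for the primary end point cannot be run as prespecified.

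The two sections also allow different primary analyses of the same 20 patients: a comparison of responder proportions, or a comparison of changes in count. The sample size is justified only for the first. At stake are whether the 85% describes the analysis that will be reported, and whether that analysis is fixed before the data are seen.

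**Working it through.** **Inputs from the power statement.** Two-sided Fisher's exact test at .05; response 80% on cromolyn and 10% on placebo; 10 per group.

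**Step 1: reproduce the stated power.** Power is the sum, over all pairs (a, b) of responder numbers with two-sided Fisher p ≤ .05, of Bin(a; 10, 0.8) × Bin(b; 10, 0.1). With b responders on placebo, significance in favour of cromolyn needs:

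| b | Prob. of b | a needed | Prob. of a | Product |
|---|---|---|---|---|
| 0 | 0.3487 | ≥5 | 0.9936 | 0.3465 |
| 1 | 0.3874 | ≥7 | 0.8791 | 0.3406 |
| 2 | 0.1937 | ≥8 | 0.6778 | 0.1313 |
| 3 | 0.0574 | ≥9 | 0.3758 | 0.0216 |
| 4 | 0.0112 | 10 | 0.1074 | 0.0012 |
| 5 | 0.0015 | 10 | 0.1074 | 0.0002 |

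The sum is 0.841. A continuity-corrected normal approximation gives 0.850. The stated 85% is reproduced.

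**Step 2: how far the power depends on the cut-off.** The document gives no count distribution, so this step rests on assumptions: the 80% and 10% hold at 15/hpf, and week-8 counts are lognormal with log SD s from 0.5 to 1.0 in both groups. The response rate at cut-off c is then Φ(z + ln(c/15)/s), with z = 0.842 for cromolyn and −1.282 for placebo.

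Example, s = 0.5 and c = 10: ln(10/15)/0.5 = −0.811. Cromolyn is Φ(0.031) = 51.2%, placebo is Φ(−2.093) = 1.8%, and exact Fisher power is 57.4%.

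| Log SD | Implied week-8 medians, cromolyn / placebo | Power at 20 | at 15 | at 10 | at 6 |
|---|---|---|---|---|---|
| 0.5 | 9.8 / 28.5 | 82.5% | 84.1% | 57.4% | 1.3% |
| 0.75 | 8.0 / 39.2 | 84.6% | 84.1% | 72.5% | 23.9% |
| 1.0 | 6.5 / 54.0 | 85.1% | 84.1% | 76.9% | 49.2% |

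**Step 3: false positives if the analysis is chosen after seeing the data.** Fisher's test is conservative at this size: its exact two-sided error is at most 1.3%, reached when both groups respond at 50%. The rest is simulated under no treatment difference. Assumptions: lognormal counts, baseline above 15/hpf, underlying baseline median 30 to 80, log SD 0.5 to 1.0, correlation 0 to 0.5, and either no shift at week 8 or an equal fall in both groups leaving about 10%, 30% or 50% at or below 15/hpf. There are 72 scenarios of 20,000 trials each. Ranges over scenarios:

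- any of three cut-offs (15, 10, 6): at most 2.8%
- Fisher at 15/hpf or one count-change t-test: about 3.5–6.7%
- raw change or log change, with no responder analysis: about 5.5–8.2%
- free choice among all five analyses: about 6–10%, the top being reached only when both groups fall so that about half are at or below 15/hpf.

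**The case against.** A responder proportion is one legitimate way to summarise a change in eosinophilia, and the power statement expressly calls the Fisher comparison the primary end-point analysis. On that reading the sections are compatible and the plan points to a responder primary. This stands: the fault is a missing definition and a missing link, not a numerical contradiction.

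It can be said that 15/hpf is the implied cut-off. The document uses it only for diagnosis and never carries it to week 8. Even if it were adopted, the count basis would remain open.

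A definition might sit in a figure. One figure under Endoscopy with biopsy and the Figure 3 timeline are not shown, so this cannot be excluded. The text introduces Figure 3 only as the study timeline.

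Three stronger readings are tempting and are not supported:

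- **The .05 level gives no protection.** Choosing the cut-off freely stays below 3%, and choosing between Fisher at 15/hpf and one count test stays near 5%. Most of the inflation comes from leaving open how a count change is analysed (raw or log scale), not from the mismatch between the two sections.
- **The 85% is wrong.** It reproduces.
- **The trial is underpowered for a change in count.** The document gives no SD, so this cannot be shown. Under the lognormal assumption, 80% against 10% corresponds to a difference in log week-8 count of 0.842 + 1.282 = 2.12 SD, for which a t-test with 10 per group has about 99% power.

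**Conclusion.** The point holds as an undefined and unlinked primary variable. In the readable text the power calculation uses a responder rate with no responder rule, while the primary outcome is a change with no stated metric. The 85% (84.1% exact) is correct arithmetic for the responder comparison and for nothing else in the plan.

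The dependence on the cut-off is the material consequence. Under the Step 2 assumptions, power hardly moves between 15 and 20/hpf, falls to 57.4–76.9% at 10 and falls below 50% at 6. Nothing in the document ties 80% and 10% to 15/hpf, so these figures show sensitivity and do not estimate the trial's power.

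The type I error inflation is modest, depends on assumed distributions, and would not by itself make the change necessary. The case for acting is that the named primary test cannot be run as prespecified and that two sections permit different primary analyses.

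**What to change.** Before unblinding, make the Primary Outcome Measure section and the power statement name the same primary variable.

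- **The choice that keeps the stated power:** histologic response at week 8, with one explicit eosinophil cut-off and one stated count basis (for example, peak count, with the biopsies it covers), compared by two-sided Fisher's exact test at .05. The change in count becomes a secondary outcome. The sponsor should confirm that 80% and 10% are the rates expected at the chosen cut-off.
- **If change in count stays primary:** name one analysis and one scale, and replace the power statement with one for that analysis, giving the assumed SD.

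The cost is wording only. The week-8 biopsies are already scheduled for all subjects, and neither choice adds a procedure. The first adds no patients; under the second, whether 10 per group suffices depends on an SD the document does not give. The drawback of the first is that a responder endpoint uses less of the information in the counts.
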